3.2 Exclusion Criteria

- 3.2.1 Patients who have had chemotherapy or radiotherapy within 4 weeks (6 weeks for nitrosoureas or mitomycin C) prior to entering the study or those who have not recovered from adverse events (AEs) due to agents administered more than 3 weeks earlier. Patients who have had prior pelvic radiation may be at increased risk for bowel perforation, and therefore may not have residual inflammatory disease of the bowel or residual bowel toxicity based on baseline imaging and clinical assessment. Palliative (limited-field) radiation therapy is permitted, if all of the following criteria are met:
 - 1) Repeat imaging demonstrates no new sites of bone metastases.
 - 2) The lesion being considered for palliative radiation is not a target lesion.
 - 3) Bowel toxicity is not expected from the target field due to increased risk of perforation
- 3.2.2 Patients who are receiving any other investigational agents.
- 3.2.3 Patients are excluded if they have had prior treatment with an anti-PD-1, anti-PD-L1, anti-PD-L2, anti-CTLA-4 antibody, or any other antibody or drug specifically targeting T-cell co-stimulation or immune checkpoint pathways.

- 3.2.4 Active brain metastasis or leptomeningeal disease. Patients with known brain metastases are allowed if metastases have been treated and there is no magnetic resonance imaging (MRI) evidence of progression for at least 12 weeks after treatment is complete and within 28 days prior to the first dose of nivolumab administration. There must also be no requirement for immunosuppressive doses of systemic corticosteroids (>10 mg/day prednisone equivalents) for at least 2 weeks prior to study drug administration.
- 3.2.5 History of allergic reactions attributed to compounds of similar chemical or biologic composition to nivolumab.
- 3.2.6 History of severe hypersensitivity reaction to any monoclonal antibody.
- 3.2.7 Uncontrolled intercurrent illness including, but not limited to, ongoing or active infection, symptomatic congestive heart failure, unstable angina pectoris, cardiac arrhythmia, or psychiatric illness/social situations that would limit compliance with study requirements.
- 3.2.8 Pregnant women are excluded from this study because the effects of nivolumab on the developing fetus are unknown. Because there is an unknown but potential risk for adverse events in nursing infants secondary to treatment of the mother with nivolumab, breastfeeding should be discontinued if the mother is treated with nivolumab.
- 3.2.9 Because the effects of nivolumab on chronic viral infection are not well known, patients should be excluded if they have known history of testing positive for human immunodeficiency virus (HIV) or known acquired immunodeficiency syndrome (AIDS) or if they have a positive test for hepatitis B virus surface antigen (HBV sAg) or hepatitis C virus ribonucleic acid (HCV antibody) indicating acute or chronic infection.
- 3.2.10 Patients with active autoimmune disease or history of autoimmune disease that might recur, which may affect vital organ function or require immune suppressive treatment including systemic corticosteroids, are excluded. These include but are not limited to patients with a history of immune related neurologic disease, multiple sclerosis, autoimmune (demyelinating) neuropathy, Guillain-Barre syndrome, myasthenia gravis; systemic autoimmune disease such as SLE, connective tissue diseases, scleroderma, inflammatory bowel disease (IBD), Crohn's, ulcerative colitis, hepatitis; and patients with a history of toxic epidermal necrolysis (TEN), Stevens-Johnson syndrome, or phospholipid syndrome should be excluded because of the risk of recurrence or exacerbation of disease. Patients with vitiligo, endocrine deficiencies including thyroiditis managed with replacement hormones including physiologic corticosteroids are eligible. Patients with rheumatoid arthritis and other arthropathies, Sjögren's syndrome and psoriasis controlled with topical medication and patients with positive serology, such as antinuclear antibodies (ANA), anti-thyroid antibodies should be evaluated for the presence of target organ involvement and potential need for systemic treatment but should otherwise be eligible.

3.2.11 Patients are permitted to enroll if they have vitiligo, type I diabetes mellitus, residual hypothyroidism due to autoimmune condition only requiring hormone replacement, psoriasis not requiring systemic treatment, or conditions not expected to recur in the absence of an external trigger (precipitating event).

3.2.12 Patients should be excluded if they have a condition requiring systemic treatment with either corticosteroids (>10 mg daily prednisone equivalents) or other immunosuppressive medications within 14 days of study drug administration. Inhaled or topical steroids and adrenal replacement doses ≤ 10 mg daily prednisone equivalents are permitted in the absence of active autoimmune disease. Patients are permitted to use topical, ocular, intra-articular, intranasal, and inhalational corticosteroids (with minimal systemic absorption). Physiologic replacement doses of systemic corticosteroids are permitted, even if ≤ 10 mg/day prednisone equivalents. A brief course of corticosteroids for prophylaxis (e.g., contrast dye allergy) or for treatment of non-autoimmune conditions (e.g., delayed-type hypersensitivity reaction caused by contact allergen) is permitted.

3.2.13 Patients who have had evidence of active or acute diverticulitis, intra-abdominal abscess, GI obstruction, fistula and abdominal carcinomatosis which are known risk factors for bowel perforation should be evaluated for the potential need for additional treatment before coming on study.

3.3 Inclusion of Women and Minorities

Every attempt will be made to enter all eligible patients into this protocol and therefore address the study objectives in a patient population representative of the population of women with advanced leiomyosarcoma of the uterus treated by participating institutions.

Please see the Planned Enrollment Report (table in Section 13.2).

4 REGISTRATION PROCEDURES (ROSTERED PROTOCOL MODEL)

4.1 Investigator and Research Associate Registration with CTEP

4.1.1 CTEP Registration Procedures

Food and Drug Administration (FDA) regulations and National Cancer Institute (NCI) policy require all investigators participating in any NCI-sponsored clinical trial to register and to renew their registration annually.

Registration requires the submission of:

- a completed ***Statement of Investigator Form*** (FDA Form 1572) with an original signature
- a current Curriculum Vitae (CV)
- a completed and signed ***Supplemental Investigator Data Form*** (IDF)
- a completed ***Financial Disclosure Form*** (FDF) with an original signature

Fillable PDF forms and additional information can be found on the CTEP website at http://ctep.cancer.gov/investigatorResources/investigator_registration.htm. For questions, please contact the **CTEP Investigator Registration Help Desk** by email at [contact].

4.1.2 CTEP Associate Registration Procedures / CTEP-IAM Account

The Cancer Therapy Evaluation Program (CTEP) Identity and Access Management (IAM) application is a web-based application intended for use by both Investigators (i.e., all physicians involved in the conduct of NCI-sponsored clinical trials) and Associates (i.e., all staff involved in the conduct of NCI-sponsored clinical trials).

Associates will use the CTEP-IAM application to register (both initial registration and annual re-registration) with CTEP and to obtain a user account.

Investigators will use the CTEP-IAM application to obtain a user account only. (See CTEP Investigator Registration Procedures above for information on registering with CTEP as an Investigator, which must be completed before a CTEP-IAM account can be requested.)

An active CTEP-IAM user account is needed to access all CTEP and CTSU (Cancer Trials Support Unit) websites and applications, and is critical to the conduct of this study, including document access, patient enrollment, and clinical data submission.

Additional information can be found on the CTEP website at http://ctep.cancer.gov/branches/pmb/associate_registration.htm. For questions, please contact the **CTEP Associate Registration Help Desk** by email at [contact].

4.2 Site Registration

This study is supported by the NCI Cancer Trials Support Unit (CTSU).

Each investigator or group of investigators at a clinical site must obtain Institutional Review Board (IRB) approval for this protocol and submit all required regulatory documents (including any protocol specific documents) to the CTSU Regulatory Office before they can be approved to enroll patients. Assignment of site registration status in the CTSU Regulatory Support System (RSS) uses extensive data to make a determination of whether a site has fulfilled all regulatory criteria including but not limited to: an active Federal Wide Assurance (FWA) number, an active

roster affiliation with the Lead Network or a participating organization, a valid IRB approval, and compliance with all protocol specific requirements.

Sites participating on the NCI CIRB initiative and accepting CIRB approval for the study are not required to submit separate IRB approval documentation to the CTSU Regulatory Office. For sites using the CIRB, IRB approval information is received from the CIRB and applied to the RSS in an automated process. Signatory Institutions must submit a Study Specific Worksheet for Local Context (SSW) to the CIRB via IRBManager to indicate their intent to open the study locally. The CIRB's approval of the SSW is then communicated to the CTSU Regulatory Office. In order for the SSW approval to be processed, the Signatory Institution must inform the CTSU which CIRB-approved institutions aligned with the Signatory Institution are participating in the study.

4.2.1 Downloading Regulatory Documents

Site registration forms may be downloaded from the 9672 protocol page located on the CTSU Web site. Permission to view and download this protocol is restricted and is based on person and site roster data housed in the CTSU RSS. To participate, Investigators and Associates must be associated with the Corresponding or Participating protocol organization in the RSS.

- Go to <https://www.ctsu.org> and log in using your CTEP IAM username and password
- Click on the Protocols tab in the upper left of your screen
- Either enter the protocol # in the search field at the top of the protocol tree, or
- Click on the By Lead Organization folder, then select LAO-MA036 and protocol #9672
- Click on LPO Documents, select the Site Registration documents link, and download and complete the forms provided. (Note: For sites under the CIRB initiative, IRB data will load to RSS as described above.)

4.2.2 Requirements For 9672 Site Registration:

- CTSU Transmittal Sheet (optional)
- IRB approval (For sites not participating via the NCI CIRB; local IRB documentation, an IRB-signed CTSU IRB Certification Form, Protocol of Human Subjects Assurance Identification/IRB Certification/Declaration of Exemption Form, or combination is accepted)

4.2.4 Checking Site Registration Status

Sites can verify their site registration status on the members' section of the CTSU website:

- Go to <https://www.ctsu.org> and log in to the members' area using your CTEP IAM username and password.
- Click on the Regulatory tab at the top of your screen.
- Click on the Site Registration subtab.
- Enter your 5-character CTEP Institution Code and click on Go.

Note: The status given only reflects compliance with IRB documentation and institutional compliance with protocol-specific requirements as outlined by the Lead Network. It does not reflect compliance with protocol requirements for individuals participating on the protocol or the enrolling investigator's status with the NCI or other affiliated networks.

4.3 Patient Registration

4.3.1 OPEN / IWRS

Patient enrollment will be facilitated using the Oncology Patient Enrollment Network (OPEN). OPEN is a web-based registration system available to users on a 24/7 basis. It is integrated with the CTSU Enterprise System for regulatory and roster data interchange and with the Theradex Interactive Web Response System (IWRS) for retrieval of patient registration/randomization assignment. Patient enrollment data entered by Registrars in OPEN / IWRS will automatically transfer to the NCI's clinical data management system, Medidata Rave.

For trials with slot reservation requirements, OPEN will connect to IWRS at enrollment initiation to check slot availability. Registration staff should ensure that a slot is available and secured for the patient before completing an enrollment.

The OPEN system will provide the site with a printable confirmation of registration and treatment information. Please print this confirmation for your records.

4.3.2 OPEN/IWRS User Requirements

OPEN/IWRS users must meet the following requirements:

- Have a valid CTEP-IAM account (*i.e.*, CTEP username and password).
- To enroll patients or request slot reservations: Be on an ETCTN Corresponding or Participating Organization roster with the role of Registrar.
- To approve slot reservations or access cohort management: Be identified to Theradex as the “Client Admin” for the study.
- Have regulatory approval for the conduct of the study at their site.

Prior to accessing OPEN/IWRS, site staff should verify the following:

- All eligibility criteria have been met within the protocol stated timeframes. Site staff should use the registration forms provided on the CTSU web site as a tool to verify eligibility.
- If applicable, all patients have signed an appropriate consent form and HIPAA authorization form.

4.4 General Guidelines

Following registration, patients should begin protocol treatment within 21 days. Issues that would cause treatment delays should be discussed with the Principal Investigator. If a patient does not receive protocol therapy following registration, the patient’s registration on the study may be canceled. The Study Coordinator should be notified of cancellations as soon as possible.

5 TREATMENT PLAN

5.1 Agent Administration

Treatment will be administered on an outpatient basis. Reported adverse events and potential risks are described in Section 7. Appropriate dose modifications are described in Section 6. No investigational or commercial agents or therapies other than those described below may be administered with the intent to treat the patient's malignancy.

5.1.1 COHORT A (nivolumab alone)- Closed to Accrual

Cohort A opened for accrual on 13-May-2015; accrual to this cohort was completed on 21-Oct-2015. All participants in Cohort A received Nivolumab monotherapy as per the below dosing instructions.

Nivolumab will be given every two weeks (± 2 days) at a dose of 3 mg/kg. Patients may be dosed no less than 12 days from the previous dose of drug.

The dosing calculations should be based on the actual body weight. If the patient's weight on the day of dosing differs by $>10\%$ from the weight used to calculate the original dose, the dose must be recalculated. Actual body weight at each visit may be used to calculate dose, as per institutional standard. All doses should be rounded as per institutional standard. There will be no dose modifications allowed.

Nivolumab is to be administered over an approximately 60-minute IV infusion, using a volumetric pump with a 0.2-1.2 micron in-line filter at the protocol-specified dose. The drug can be diluted with 0.9% normal saline for delivery but the total drug concentration of the solution cannot be below 0.35 mg/mL. It is not to be administered as an IV push or bolus injection. At the end of the infusion, flush the line with a sufficient quantity of normal saline. .

5.1.2 COHORT B (nivolumab and ipilimumab)

Cohort B explores combination therapy with nivolumab and ipilimumab. All participants enrolled to this cohort will receive nivolumab in combination with ipilimumab as per the dosing instructions below.

Nivolumab will be given every three weeks (± 2 days) at a dose of 3 mg/kg together with ipilimumab at a dose of 1 mg/kg for 4-cycles. Starting at cycle 5, nivolumab will be given as a monotherapy every two weeks at a dose of 3 mg/kg. Patients may be dosed no less than 12 days from the previous dose of drug. The dosing calculations should be based on the actual body weight. If the patient's weight on the day of dosing differs by $>10\%$ from the weight used to calculate the original dose, the dose must be recalculated. Actual body weight at each visit may be used to calculate dose, as per institutional standard. All doses should be rounded as per institutional standard. There will be no dose modifications allowed.

Nivolumab is to be administered over an approximately 60-minute IV infusion, using a volumetric pump with a 0.2-1.2 micron in-line filter at the protocol-specified dose. The drug can be diluted with 0.9% normal saline for delivery but the total drug concentration of the solution cannot be below 0.35 mg/mL. It is not to be administered as an IV push or bolus injection. At the end of the infusion, flush the line with a sufficient quantity of normal saline.

Ipilimumab injection can be used for IV administration without dilution after transferring to a PVC (polyvinyl chloride), non-PVC/non-DEHP (di-(2-ethylhexyl)phthalate) or glass containers and is stable for 24 hours at 2-8°C or room temperature/room light (RT/RL). Ipilimumab is to be administered as a 90-minute IV infusion, using a volumetric pump with a 0.2 to 1.2 micron in-line filter at the protocol-specified dose. The drug can be diluted with 0.9% normal saline or 5% dextrose injection to concentrations between 1 mg/mL and 4 mg/mL. It is not to be administered

as an IV push or bolus injection. Care must be taken to assure sterility of the prepared solutions, since the drug product does not contain any antimicrobial preservatives or bacteriostatic agents. At the end of the infusion, flush the line with a sufficient quantity of normal saline or 5% dextrose solution.

Separate infusion bags and filters must be used for each infusion of nivolumab and ipilimumab. Nivolumab is to be administered first. The nivolumab infusion must be promptly followed by a saline flush to clear the line of nivolumab before starting the ipilimumab infusion.

5.1.3 Other Modality(ies) or Procedures

Not applicable

5.1.4 Investigational Imaging Agent Administration

Not applicable

5.2 Definition of Dose-Limiting Toxicity

Not applicable

5.3 General Concomitant Medication and Supportive Care Guidelines

Nivolumab is a human monoclonal antibody and as such is not expected to be metabolized by cytochrome P450 (CYP) enzymes or other typical drug metabolizing enzymes. Thus, it is not expected to have any effect on CYP or other drug metabolizing enzymes in terms of inhibition or induction, and is, therefore, not expected to induce this type of PK-based drug interactions.

5.4 Duration of Therapy

In the absence of treatment delays due to adverse event(s), treatment may continue for up to 46 doses in Cohort A or until one of the following criteria applies. In Cohort B, treatment may continue for up to 4 doses of combination therapy (nivolumab + ipilimumab), and up to 46 doses of nivolumab monotherapy after the combination therapy, or until one of the following criteria applies:

- Disease progression, as per section 5.9
- Intercurrent illness that prevents further administration of treatment,
- Any patients who require additional immune suppressive treatment beyond steroids should go off study treatment
- Unacceptable adverse event(s) which include the following (see also section 6 and

specific algorithms in Appendix E):

- Any grade 2 drug-related uveitis or eye pain or blurred vision that does not respond to topical therapy and does not improve to Grade 1 severity within the re-treatment period OR requires systemic treatment
- Patients requiring > two dose delays for the same type of event should go off protocol therapy.
- Any adverse event, laboratory abnormality, or intercurrent illness which, in the judgment of the investigator, presents a substantial clinical risk to the subject with continued study drug dosing
- Any dosing interruption lasting >6 weeks, with the following exceptions:
- Patients being tapered after high dose corticosteroids over one month followed by a two-week observation period will be allowed an additional two weeks to restart treatment (a maximum eight week interruption).
- Dosing interruptions >6 weeks that occur for non-drug-related reasons may be allowed if approved by the Investigator. Prior to re-initiating treatment in a subject with a dosing interruption lasting >6 weeks, the Principal Investigator must be consulted.
- Grade 3 drug-related autoimmune or inflammatory events including uveitis, pneumonitis, diarrhea, colitis, neurologic adverse events, hypersensitivity reaction, or infusion reaction of any duration requires discontinuation except as noted below:
- Any other grade 3 non-skin, drug-related AE lasting >7 days including fatigue.
- Any grade 3 or 4 drug-related laboratory abnormality or electrolyte abnormality, not associated with underlying organ pathology, that does not require treatment except for electrolyte replacements **does not** require treatment discontinuation.
- Grade 3 amylase or lipase abnormalities that are not associated with diabetes mellitus (DM), associated liver or gall bladder inflammation clinical manifestations of pancreatitis and which decrease to \leq Grade 2 within 1 week of onset **may** resume study treatment when resolved.
- Any grade 4 events except as noted above.
- Patient decides to withdraw from the study, or
- General or specific changes in the patient's condition render the patient unacceptable for further treatment in the judgment of the investigator.

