5.8 Treatment of Nivolumab or Ipilimumab Related Infusion Reactions

Since nivolumab and ipilimumab contains only human immunoglobulin protein sequences, it is unlikely to be immunogenic and induce infusion or hypersensitivity reactions. However, if such a reaction were to occur, it might manifest with fever, chills, rigors, headache, rash, urticaria, angioedema, pruritis, arthralgias, hypo- or hypertension, bronchospasm, or other symptoms.

All Grade 3 or 4 infusion reactions should be reported as an SAE if criteria are met. Infusion reactions should be graded according to NCI CTCAE version 5.0 guidelines.

Treatment recommendations are provided below and may be modified based on local treatment standards and guidelines as medically appropriate:

For Grade 1 symptoms: (Mild reaction; infusion interruption not indicated; intervention not indicated)

Remain at bedside and monitor subject until recovery from symptoms. Infusion rate may be slowed. If the infusion is interrupted, then restart the infusion at 50% of the original infusion rate when symptoms resolve; if no further complications ensue after 30 minutes, the rate may be increased to 100% of the original infusion rate. Monitor patient closely.

The following prophylactic premedications are recommended for future infusions: diphenhydramine 50 mg (or equivalent) and/or paracetamol 325 to 1000 mg (acetaminophen) at least 30 minutes before additional nivolumab administrations, slowing infusion rate as above.

For Grade 2 symptoms: (Moderate reaction requires therapy or infusion interruption but responds promptly to symptomatic treatment [e.g., antihistamines, non-steroidal anti-inflammatory drugs, narcotics, corticosteroids, bronchodilators, IV fluids]; close observation for recurrence and treatment medications may need to be continued for 24-48 hours).

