Stop the nivolumab infusion, begin an IV infusion of normal saline, and treat the subject with diphenhydramine 50 mg IV (or equivalent) and/or paracetamol 325 to 1000 mg (acetaminophen); remain at bedside and monitor patient until resolution of symptoms. Corticosteroid or bronchodilator therapy may also be administered as appropriate. If the infusion is interrupted, then restart the infusion at 50% of the original infusion rate when symptoms resolve; if no further complications ensue after 30 minutes, the rate may be increased to 100% of the original infusion rate. Monitor patient closely. If symptoms recur, then no further nivolumab will be administered at that visit. Administer diphenhydramine 50 mg IV, and remain at bedside and monitor the patient until resolution of symptoms. The amount of study drug infused must be recorded on the electronic case report form (eCRF). The following prophylactic premedications

are recommended for future infusions: diphenhydramine 50 mg (or equivalent) and (acetaminophen) (or paracetamol) 325 to 1000 mg should be administered at least 30 minutes before additional nivolumab administrations. If necessary, corticosteroids (recommended dose: up to 25 mg of IV hydrocortisone or equivalent) may be used.

For Grade 3 or Grade 4 symptoms: (Severe reaction), Grade 3 symptoms: prolonged [*i.e.*, not rapidly responsive to symptomatic medication and/or brief interruption of infusion]; recurrence of symptoms following initial improvement; hospitalization indicated for other clinical sequelae [*e.g.*, renal impairment, pulmonary infiltrates]).

Grade 4 symptoms: (life threatening; pressor or ventilatory support indicated).

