Immediately discontinue infusion of nivolumab. Begin an IV infusion of normal saline, and treat the subject as follows. Recommend bronchodilators, epinephrine 0.2 to 1 mg of a 1:1,000 solution for subcutaneous administration or 0.1 to 0.25 mg of a 1:10,000 solution injected slowly for IV administration, and/or diphenhydramine 50 mg IV with methylprednisolone 100 mg IV (or equivalent), as needed. Patient should be monitored until the investigator is comfortable that the symptoms will not recur. Nivolumab will be permanently discontinued. Investigators should follow their institutional guidelines for the treatment of anaphylaxis. Remain at bedside and monitor patient until recovery from symptoms. In the case of late-occurring hypersensitivity symptoms (*e.g.*, appearance of a localized or generalized pruritis within 1 week after treatment), symptomatic treatment may be given (*e.g.*, oral antihistamine, or corticosteroids).

Please note that late occurring events including isolated fever and fatigue may represent the presentation of systemic inflammation. Please evaluate accordingly.

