| ≤ Grade 1 | Asymptomatic TSH elevation*; continue at investigator discretion with evaluation of thyroid function. |
| Grade 2 | Hold until patients are on a stable replacement hormone regimen. If treated with steroids, patients must be stable off steroids for two weeks. Resume at same dose level. |
| Grade 3 | Off protocol therapy. |
| Grade 4 | Off protocol therapy |
| 
Note all patients with symptomatic pituitary enlargement, exclusive of hormone deficiency, but including severe headache or enlarged pituitary on MRI should be considered grade 3 events. Isolated thyroid or testosterone deficiency may be treated as grade 2 if there are no other associated deficiencies and adrenal function is monitored.
 
Please evaluate pituitary function before beginning steroid therapy or replacement therapy of any kind.
 
*Note patients with thyroiditis may be retreated on replacement therapy. Patients must be evaluated to rule out pituitary disease prior to initiating thyroid replacement.
 | |
| 
Recommended management: TSH, T3, and T4 will be collected at baseline. After baseline, TSH will be collected every 6 weeks; T3/T4 will be collected when indicated. See Endocrine Management Algorithm
 | |

| Renal | Management/Next Dose for Nivolumab and combination Nivolumab/ipilimumab |
|--|--|
| ≤ Grade 1 | Continue at same dose at investigator discretion |
| Grade 2 | Hold pending evaluation. Resume at same dose level at investigator discretion. |
| Grade 3 | Off study treatment |
| Grade 4 | Off study treatment |
| 
Patients with fever should be evaluated as clinically appropriate. Patients may experience isolated fever during infusion reactions or up to several days after infusion. Evaluation over the course of 1-2 weeks should be done for other autoimmune events that may present as fever
 | |
| Infusion reaction | Management/Next Dose for Nivolumab and combination Nivolumab/ipilimumab |
| ≤ Grade 1 | Continue at slower rate at investigator discretion |
| Grade 2 | Hold until ≤ Grade 1. Resume at same dose level |
| Grade 3 | Hold until ≤ Grade 1. Resume at same dose level |
| Grade 4 | Off protocol therapy |

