| 
Patients with fever should be evaluated as clinically appropriate. Patients may experience isolated fever during infusion reactions or up to several days after infusion. Evaluation over the course of 1-2 weeks should be done for other autoimmune events that may present as fever
 
See section 5.8- Treatment of Nivolumab or Ipilimumab Infusion reactions
 | |

| Fever | Management/Next Dose for Nivolumab |
|--------------|---|
| ≤ Grade 1 | Evaluate and continue at same dose level |

| Fever | Management/Next Dose for Nivolumab |
|--|--|
| Grade 2 | Continue at investigator discretion |
| Grade 3 | Hold until \leq Grade 1. Resume at same dose level at investigator discretion. |
| Grade 4 | Off protocol therapy |
| Patients with fever should be evaluated as clinically appropriate. Patients may experience isolated fever during infusion reactions or up to several days after infusion. Evaluation over the course of 1-2 weeks should be done for other autoimmune events that may present as fever | |
| See section 5.8: Treatment of Nivolumab or Ipilimumab Infusion reactions | |

If treatment is delayed >8 weeks for an adverse event, the patient must be permanently discontinued from study therapy.

Patients requiring high dose steroid treatment for autoimmune or inflammatory events should be managed as described in section 5.7, except for a short course of tapering steroids for infusion reaction, skin rash, or endocrine events.

Patients with grade 3 thyroiditis and skin rash may continue therapy as for grade 2 events with resolution and stable replacement treatment.

Patients with thyroiditis or hypopituitarism who are stable as above may be restarted with replacement hormones including thyroid hormone and physiologic doses of corticosteroids. Please note that grade for hypophysitis with symptoms of headache, visual, or neurologic changes or radiologic evidence of pituitary enlargement and other CNS events such as aseptic meningitis or encephalitis should be considered grade 3 events.

Any patient who requires additional immune suppressive treatment beyond steroids should go off protocol therapy.

Patients requiring $>$ two dose delays, other than for evaluation for the same event, should go off protocol therapy. Patients may be dose-delayed for evaluation and restarted depending on results.

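### The section 6 table tells sites to re-dose after a Grade 3 infusion reaction, which sections 5.4 and 5.8 treat as a reason to stop

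*Combined protocol and SAP*

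**What the plan says.** Three places in the combined protocol and SAP give a dosing instruction for a Grade 3 infusion reaction.

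- **Section 5.4 (Duration of Therapy)**, among the unacceptable adverse events that end treatment: "Grade 3 drug-related autoimmune or inflammatory events including uveitis, pneumonitis, diarrhea, colitis, neurologic adverse events, hypersensitivity reaction, or infusion reaction of any duration requires discontinuation". The sentence goes on to allow for exceptions listed below it.
- **Section 5.8 (infusion reactions)** treats the two severe grades together, in a paragraph that opens "For Grade 3 or Grade 4 symptoms: (Severe reaction". Within that instruction it states: "Nivolumab will be permanently discontinued".
- **Section 6 (Dosing Delays/Dose Modifications)**, in the infusion-reaction table headed for nivolumab and for the combination: "Grade 3 | Hold until ≤ Grade 1. Resume at same dose level". The Grade 2 row carries the same instruction: "Grade 2 | Hold until ≤ Grade 1. Resume at same dose level". Only Grade 4 goes off protocol therapy. A note under the table reads "See section 5.8- Treatment of Nivolumab or Ipilimumab Infusion reactions".

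**The concern.** A site cannot follow all three instructions. One has the patient dosed again at full dose once the reaction has settled to Grade 1 or less. The other two end treatment, or at least end nivolumab.

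What is at stake is re-exposure after a severe reaction. Section 5.8 describes Grade 3 as a reaction that is prolonged, that returns after first improving, or that calls for hospital admission. The treatments it suggests include epinephrine, bronchodilators and intravenous methylprednisolone. A grade-by-grade table of what to do with the next dose is a natural place for site staff to look, and here it gives the less protective answer.

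**Working it through.** No arithmetic applies. The check is whether any text in the protocol reconciles the row with 5.4 and 5.8.

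1. **The exceptions in 5.4.** The items below the rule concern other Grade 3 non-skin events lasting more than 7 days, laboratory or electrolyte abnormalities, amylase or lipase elevations, and Grade 4 events. The first is limited to events other than those already named. The rest concern different findings or a different grade. None exempts a Grade 3 infusion reaction.

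2. **The drug-related qualifier.** 5.4 is limited to drug-related events and the section 6 row is not. That does not separate them, because an infusion reaction is by its nature a reaction to the infused agent. 5.8 carries no such qualifier.

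3. **The cross-references.** 5.4 introduces its adverse-event list with a pointer to section 6, and the section 6 table points to 5.8. Neither says which text governs. A reader who follows the table's pointer arrives at the opposite order. In another section 6 table, for immunologically mediated events, Grade 3 goes off protocol therapy and 5.4 is named as the source of exceptions. The infusion-reaction row is out of line with that.

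4. **Restarting under 5.7.** Where 5.7 names Grade 3 events after which nivolumab may be restarted, it names skin rash and thyroiditis. Infusion reaction is not among them.

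5. **The single-agent option in 5.7.** After a Grade 2 or 3 event that ends the combination, the PI may consider nivolumab alone at the same dose. Compared with the row:
   - the option needs a PI decision; the row needs none;
   - the option needs resolution to baseline; the row accepts Grade 1 or less;
   - the option drops ipilimumab; the row covers the combination and does not.

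   The option also concerns the combination period only. For nivolumab alone (Cohort A, and Cohort B from cycle 5) it has no role.

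6. **The steroid rule as a backstop.** 5.7 discontinues nivolumab in patients given steroids for Grade 3 or higher events. Section 6, however, says that patients on high-dose steroids "should be managed as described in section 5.7, except for a short course of tapering steroids for infusion reaction, skin rash, or endocrine events". A patient given a short tapering course for an infusion reaction may therefore never reach the 5.7 stop.

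**Result for a Grade 3 infusion reaction:** 5.4, discontinue; 5.8, permanently discontinue nivolumab; section 6, hold and then resume the same dose. Nothing in the protocol reconciles these.

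**The case against.** The best case for the plan has four parts.

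- **5.8 is flexible.** It says: "Treatment recommendations are provided below and may be modified based on local treatment standards and guidelines as medically appropriate". Its stop could be read as advice. That is fair as far as 5.8 goes, but the 5.4 stop carries no such allowance.
- **5.4 is not absolute in cycles 1 to 4.** The 5.7 single-agent option excludes only renal, CNS and pulmonary toxicity, so on its face it could reach an infusion reaction during the combination period. This stands: it would be too strong to say that every Grade 3 infusion reaction ends all treatment under every section. It does not rescue the row, whose conditions differ on all three counts above.
- **There are safeguards.** The table sends the reader to 5.8, and both 5.4 and section 6 stop treatment when the investigator judges continued dosing to carry substantial risk. These lower the practical risk but leave the wrong instruction in place.
- **The event may be rare.** 5.8 calls infusion and hypersensitivity reactions unlikely. The nivolumab risk list (7.1.2.1) puts infusion related reaction in its column for 20% or less, which is not specific to Grade 3, and a footnote says high-grade reactions have been observed. So the event is recognised, but its frequency cannot be taken from the documents.

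**Conclusion.** The contradiction is real and wrong as written. It must be corrected for patient safety. Its extent is one row of one table set against two other sections. How many patients it could affect is unknown, because no Grade 3 rate is given, and counting planned doses would say nothing about how often the row is used. The conclusion rests only on the wording of 5.4, 5.7, 5.8 and section 6.

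A reader might infer more than the documents support in three ways:

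- **That the Grade 3 diarrhea/colitis row in section 6 is the same error.** It also allows resumption, but it is not limited by cause and directs evaluation for infectious, ischemic and other causes, whereas 5.4 concerns drug-related events. The two can be read together. The GI algorithm on which the row relies is a figure that is not shown, so an error cannot be established.
- **That the 5.7 single-agent option is already barred for this event.** 5.8 points that way, but 5.7 does not exclude infusion reactions. Barring the option is a clinical decision.
- **That the trial's statistics are affected.** The two-stage operating characteristics, the decision rules and the response and toxicity analyses do not change.

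**What to change.** **Required.** In the section 6 infusion-reaction table, change the Grade 3 entry to off protocol therapy, and notify sites.

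**Optional, for the clinical team.** State in 5.8 what happens to ipilimumab after a Grade 3 infusion reaction, since its permanent stop names only nivolumab. State also whether the 5.7 single-agent option applies to this event.

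**Editorial.** Section 6 twice cites 5.6 for the rules on resuming treatment. Section 5.6 covers removal from study; the resumption rules are in 5.7. Correct both references.

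A general sentence giving 5.4 precedence is not advised, because it could override the continuation after Grade 3 thyroiditis that 5.7 and section 6 deliberately allow.

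**Cost.** A text amendment to one row, with one or two optional sentences and two corrected references, plus a site memo. Patients lose only the re-dosing that the row offers and that 5.4 and 5.8 already withdraw. Sample size, decision rules and analyses stay as they are.
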